7.1.3 Physical Examination

Brief physical examination will include skin, eyes, oral mucosa, cardiac, and respiratory. A brief physical examination will be conducted at all study visits. Body weight will be also examined at the Baseline (Month 18 of TTP488-301), Month 6, Month 12, Month 18, and Month 24 study visits.

7.1.4 Neurological Examination

Brief neurological examination will include meningeal irritation assessment, cranial nerves, motor and sensory function, coordination, deep tendon reflexes, stance and gait. Brief neurological examination will be conducted at all study visits.

7.1.5 Laboratory

7.1.5.1 Standard Safety Laboratory Tests

Unless noted otherwise, the following safety laboratory tests will be performed at Baseline (Month 18 of TTP488-301), Months 6, 12, 18, and 24 or at time of premature discontinuation. All routine laboratory tests will be analyzed by a central laboratory, which will provide instructions and supplies.

Hematology	Chemistry
Hemoglobin	BUN and Creatinine
Hematocrit RBC count	Glucose
Platelet count WBC count	Calcium
MCV	Sodium
Total neutrophils (Abs)	Potassium
Eosinophils (Abs)	Chloride
Monocytes (Abs)	Total CO2 (Bicarbonate)
Basophils (Abs)	AST
Lymphocytes (Abs)	ALT
	GGT
	LDH
	Total Bilirubin
	Alkaline phosphatase
	Uric acid
	Albumin
	Total protein
	HbA1c

7.1.5.2 Assessment of Potential Cases of Drug Induced Liver Injury

Abnormal values in aspartate transaminase (AST) and/or alanine transaminase (ALT) concurrent with abnormal elevations in total bilirubin that meet the criteria outlined below, in the absence of other causes of liver injury, are considered potential cases of drug-induced liver injury. These events should be considered important medical events, and reported as serious adverse events.

Participants who present with the following laboratory abnormalities should be evaluated further to definitively determine the etiology of the abnormal laboratory values:

- a. Participants with AST or ALT baseline values within the normal range who subsequently present with AST or ALT ≥ 3 times the upper limit of normal concurrent with a total bilirubin ≥ 2 times the upper limit of normal with no evidence of 1) hemolysis, 2) cholestasis (elevated alkaline phosphatase ≥ 2 times the upper limit of normal or not available) or 3) Gilbert's Syndrome (common benign condition associated with intermittent elevations of primarily indirect, unconjugated, bilirubin to about 2 X upper limit of normal.)
- b. Participants with pre-existing AST or ALT baseline values above the normal range who subsequently present with AST or ALT ≥ 2 times the baseline values and ≥ 3 times the upper limit of normal concurrent with a total bilirubin ≥ 2 times the upper limit of normal

with no evidence of 1) hemolysis, 2) cholestasis (elevated alkaline phosphatase ≥ 2 times the upper limit of normal or not available) or 3) Gilbert's Syndrome (common benign condition associated with intermittent elevations of primarily indirect, unconjugated, bilirubin to about 2 X upper limit of normal.)

Increases defined above should be confirmed with repeat testing within 48 to 72 hours. In addition to repeating AST and ALT, laboratory tests should include albumin, amylase, creatine kinase, total bilirubin, direct and indirect bilirubin, gamma-glutamyl transferase (GGT), international normalized ratio (INR) and alkaline phosphatase. Symptoms should be assessed. The medical monitor should be contacted to discuss the patient's condition.

Close observation should be immediately initiated if symptoms persist and/or repeat testing confirm the abnormalities described above. Evaluation should include repeating laboratory tests (two or three time weekly; frequency may decrease to once a week or less if abnormalities stabilize or trial drug is discontinued and the subject is asymptomatic), and a detailed medical history and physical assessment. A detailed history, including relevant information, such as history of symptoms or concurrent illnesses, concomitant medication use (including review of acetaminophen use and herbal/dietary supplements), alcohol consumption, recreational drug use and special diets. Additionally family history, sexual history, travel history, history of contact with a jaundiced subject, surgery, blood transfusion, history of liver or allergic disease, and work exposure, should be collected. Ruling out acute hepatitis A, B, C, D, and E infection, autoimmune or alcoholic hepatitis, NASH, hypoxic/ischemic hepatopathy, Epstein-Barr virus, cytomegalovirus, herpes simplex virus, toxoplasmosis, varicella, parvovirus and biliary tract disease (gall bladder/ductal imaging may be warranted).

All cases confirmed on repeat testing, with no other cause for LFT abnormalities identified at the time should be considered potential drug induced liver injury irrespective of availability of all the results of the investigations performed to determine etiology of the abnormal LFTs.

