8.0 ADVERSE EVENT REPORTING

8.1 ADVERSE EVENTS

An adverse event (AE) is any untoward medical occurrence in a clinical study participant administered a pharmaceutical product. Study drug treatment does not necessarily have a causal relationship with the AE. An AE, therefore, can be any unfavorable change in structure, function or chemistry (including abnormal clinical lab results, or ECG findings), symptoms, signs, or diseases temporally associated with the use of a medicinal (investigational) product, whether or not related to the medicinal (investigational) product, as defined by ICH.

The criteria for determining whether an abnormal objective test finding should be reported as an adverse event are as follows:

- Test result is associated with accompanying symptoms, and/or
- Test result requires additional diagnostic testing or medical/surgical intervention, and/or
- Test result leads to a change in study dosing or discontinuation from the study, significant additional concomitant drug treatment, or other therapy, and/or
- Test result is considered to be an adverse event by the investigator or sponsor.

Repeating an abnormal test, in the absence of any of the above conditions, does not constitute an adverse event. Any abnormal test result that is determined to be an error does not require reporting as an adverse event.

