8.5 SERIOUS ADVERSE EVENTS

A serious adverse event (SAE) is any AE that is fatal or life-threatening (see below), results in persistent or significant disability (see below) or incapacity, requires inpatient hospitalization or prolongation of an existing hospitalization, or is a congenital anomaly/birth defect.

Other important medical events that may not result in death, be life-threatening or require hospitalization should also be considered SAEs when, based upon appropriate medical judgment, they may jeopardize the study participant and may require medical or surgical intervention to prevent one of the outcomes listed above. Examples of such medical events include allergic bronchospasm requiring intensive treatment in an emergency room or at home or convulsions that do not result in inpatient hospitalization.

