8.7.1 Serious Adverse Events Reporting Requirements

Knowledge of a SAE occurring or worsening in a subject at any time during the trial must be reported within 24 hours to the Safety Monitor. The site is responsible for reporting the event to the relevant IRB/REB in accordance with the IRB or REB's specific requirements for reporting SAEs. The Principal Investigator or designee should not wait to receive additional or follow-up information before an initial notification is made to the Sponsor.

Instructions related to SAE reporting, along with reporting forms and Sponsor contact information will be provided by the Sponsor to the Study Site and should be maintained in the Study Site File (SSF).

Reports relative to the subject's subsequent course must be submitted to the Safety Monitor until the event has subsided or, in the case of permanent impairment, until the condition stabilizes. These reports need not be submitted within 24 hours of first knowledge of each item of new information, unless the new information results in a change in diagnosis or represents a significant worsening of the subject's condition.

At any time following the study, the PI or designee should immediately notify the Sponsor and the IRB/REB if he/she learns of the occurrence of any malignancy involving the participant of a clinical trial or of any congenital anomaly in an offspring of a participant.

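### On its plain wording, the liver-injury criterion counts a missing alkaline phosphatase result as cholestasis, so the subject falls outside the potential-DILI and SAE rule

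*Protocol*

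**What the plan says.** Protocol 7.1.5.2 has two limbs. Limb (a), for subjects with normal baseline AST or ALT, requires AST or ALT ≥3 × ULN together with total bilirubin ≥2 × ULN. Limb (b), for subjects with a raised baseline, adds that AST or ALT must be at least twice baseline. Both limbs require that there be no evidence of hemolysis, cholestasis or Gilbert's syndrome. The bracket that explains cholestasis is the same in both: alkaline phosphatase at least 2 "times the upper limit of normal or not available) or 3".

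Three things hang on these limbs:

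- **SAE status.** Cases that meet the criteria and have no other cause of liver injury are potential DILI: "These events should be considered important medical events, and reported as serious adverse events". Under Protocol 8.7.1 an SAE "must be reported within 24 hours to the Safety Monitor".
- **Repeat testing.** "Increases defined above should be confirmed with repeat testing within 48 to 72 hours". The repeat panel includes alkaline phosphatase, and the medical monitor is to be contacted.
- **Final classification.** The section closes by treating cases confirmed on repeat, with no other cause found by then, as potential DILI "irrespective of availability of all the results of the investigations performed to determine etiology of the abnormal LFTs".

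SAP 5.3.4 summarizes and lists subjects with AST or ALT ≥3 × ULN and bilirubin ≥2 × ULN. It has no alkaline phosphatase term.

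**The concern.** The cholestasis exclusion exists because a raised alkaline phosphatase offers another explanation for the bilirubin rise. A result that was never obtained offers no explanation. Yet the phrase about unavailability stands inside the bracket that defines the excluding condition, so on the plain wording an absent value removes the subject from the criterion just as a high value does.

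At stake is the one rule in the protocol that makes this laboratory pattern an SAE without anyone having to exercise judgment. Long-term safety is the primary objective, and Protocol 9.3 names the proportion of patients meeting DILI criteria as a safety variable. A liver rule that defaults to exclusion when data are missing errs in the less safe direction.

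**Working it through.** The documents give no figure to reproduce here. The check is of the logic of the rule, followed by a comparison of the texts.

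**1. The rule as a formula.** Limb (a) is met when all of these hold: AST or ALT ≥3 × ULN; bilirubin ≥2 × ULN; no hemolysis; no Gilbert's syndrome; no cholestasis. Cholestasis is then read in two ways:

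- As worded: alkaline phosphatase (ALP) ≥2 × ULN, *or* ALP missing.
- Corrected: ALP present *and* ≥2 × ULN.

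**2. Truth table.** Take a subject with normal baseline enzymes, both rises, no hemolysis and no Gilbert's syndrome, and vary only ALP:

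| ALP (× ULN) | Limb (a) as worded | Limb (a) corrected | SAP 5.3.4 |
|---|---|---|---|
| 1.0 | met | met | listed |
| 1.9 | met | met | listed |
| 2.0 | not met | not met | listed |
| 3.0 | not met | not met | listed |
| missing | **not met** | **met** | listed |

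One row of five changes. Limb (b) carries the same bracket, so once its extra condition on baseline is satisfied it gives the same column.

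**3. The repeat-test trigger.** The sentence on repeat testing refers back to the increases defined above it. If that means only the enzyme and bilirubin rises, the subject with missing ALP is still retested, and the repeat should supply the value. If it means the increases as defined by the limbs, exclusions included, this subject does not qualify, and the repeat that would fill the gap is not called for. The text does not settle which is meant.

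**4. Comparison with the other two texts.**

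- The closing paragraph of Protocol 7.1.5.2 says that outstanding results do not block classification. It concerns the later work-up of cause and reaches only cases already confirmed on repeat. It shows the principle but does not repair the limbs, least of all if the repeat was never triggered.
- SAP 5.3.4 lists the subject in every row of the table. The tabulated liver results therefore do not depend on the bracket; the protocol's SAE rule does.

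**5. How often.** Under Protocol 7.1.5.1, "All routine laboratory tests will be analyzed by a central laboratory", and ALP is on the same chemistry list as AST, ALT and bilirubin. It should seldom be missing when those are reported. SAP 6.5 allows for laboratory data from visits outside the protocol, and nothing guarantees ALP there. The documents give no rate for the combined rise or for missing ALP, so I give no expected count.

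**The case against.** The best counter-argument is that the bracket was meant the other way. The governing words ask for evidence of cholestasis, a missing result is not evidence, and the section's closing paragraph shows that missing data were not meant to clear a case. That intent is plausible, and an investigator may well read it so. But the bracket does not say it, and an SAE trigger that two sites can read in opposite directions needs correcting whichever meaning was intended.

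A reader might also infer a fixed reporting delay: with ALP below 2 × ULN the SAE goes in within 24 hours of the initial result, and with ALP missing it waits for the repeat, two to three days later (48/24 = 2, 72/24 = 3). The documents do not support that figure. SAE status also requires that no other cause be present, the increases are to be confirmed, and the closing paragraph classifies cases after confirmation. If classification follows confirmation for everyone, the bracket need cause no such delay. If it comes before, there may be one. The figure also assumes the looser reading of the repeat trigger while holding the bracket to its letter.

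A reader might further infer that cases would go unseen. That is not supported either:

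- Protocol 8.1 makes a finding an AE when "Test result requires additional diagnostic testing or medical/surgical intervention".
- Protocol 8.5 keeps judgment-based reporting open: important medical events "should also be considered SAEs when, based upon appropriate medical judgment" they may put the participant at risk.
- Protocol 9.6 provides for data monitoring committee review of safety data, and SAP 4.2 for medically qualified review of laboratory listings.
- SAP 5.3.4 lists the subject, and SAP Section 10 flags AST or ALT above 3 × ULN.

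These safeguards stand, and they limit the harm. The AE and SAE routes rest on a case-by-case assessment or lack the automatic SAE status that 7.1.5.2 was written to give.

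**Conclusion.** The point holds as a wording defect of minor severity. On the plain reading, a subject with both rises and no ALP result fails limbs (a) and (b), and so falls outside potential DILI and the SAE instruction. On a strict reading the subject may also fall outside the 48 to 72 hour repeat. This sits badly with the closing paragraph of the same section and with SAP 5.3.4, neither of which lets a missing ALP exclude a case.

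The size is one pattern, missing ALP, in each limb. It should be rare because ALP shares a panel with the other tests. The conclusion rests only on the grammar of the bracket. It assumes nothing about event rates, and no length of reporting delay can be attached to it. The planned liver tabulation is unaffected.

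**What to change.** In Protocol 7.1.5.2 (a) and (b), delete the last three words inside the cholestasis bracket, those that refer to an unavailable result. Then add one sentence: *A missing alkaline phosphatase does not exclude a case.* Because the repeat panel already includes ALP, nothing more is needed to obtain the value, provided the added sentence makes clear that such a subject meets the limb and so goes to repeat testing. SAP 5.3.4 needs no change.

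Classification at every non-missing ALP value stays the same. The downside is an occasional extra repeat panel or SAE report for a subject who turns out to be cholestatic, which is the safer error in a liver rule. In a running study the edit needs IRB/REB approval as an amendment (Protocol 12.1) and could wait for the next one planned. SAP 1.5 records that this study was terminated early, so the main benefit is wherever this text is reused.

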7.2 NEUROPSYCHOLOGICAL ASSESSMENTS

The following cognitive/functional/global test batteries will be conducted at selected time points as described below and in the Schedule of Activities. Participants should not have initiated treatment with a behavioral medication within 1 week of next clinical assessment. If there is any condition that, in the opinion of the investigator, may jeopardize the accurate evaluation of participant's function, participants should not receive neuropsychological tests, and reserve an

additional visit to evaluate function within the allowance of the visit window. Neuropsychological assessments should not be performed if the patient is fasting. The same rater should follow a particular participant for any given assessment for the duration of the study whenever possible. It is recommended that the scales be administered in the following order if they are specified to occur at the same visit: ADAS-cog, MMSE, CDR, ADCS-ADL, COWAT, CFT, Trail Making Test (Versions A and B), NPI, RUD Lite, and DEMQOL.

The CDR may be done on a separate proximal visit day to avoid patient fatigue. It is acceptable for the CDR, ADCS-ADL, and the NPI to be performed together on a separate visit day from the other cognitive assessments. All cognitive assessments must be performed by a trained rater.

7.2.1 Cognitive Assessments

Alzheimer's Disease Assessment Scale - Cognitive Subscale 70 point (ADAS-cog):

The ADAS-cog is a structured scale (approximately 40 minutes to complete) that evaluates memory, orientation, attention, reasoning, language and constructional praxis (Rosen, 1984). The ADAS-cog scoring range for the version used in this study is from 0 to 70, with higher scores indicating greater cognitive impairment. The ADAS-cog will be conducted at Baseline (Month 18 of TTP488-301) and at Months 3, 6, 9, 12, 18, and 24 or in the event of early termination. The ADAS-cog should always be administered prior to other cognitive measures.

Mini Mental State Examination (MMSE): The MMSE is a brief 30-point test that is used to assess cognition (Folstein, 1975). It is commonly used to screen for dementia. In the time span of about 10 minutes, it samples various functions, including arithmetic, memory and orientation. The MMSE will be administered at Baseline (Month 18 of TTP488-301), and at Months 6, 12, 18, and 24 or in the event of early termination. Scores range from 0-30 with lower scores indicating greater cognitive impairment.

Controlled Oral Word Association Test (COWAT): The COWAT is a measure of verbal fluency in which the participant is asked to generate orally as many words as possible that begin with the letters “F”, “A”, and “S”, excluding proper names and different forms of the same word. (Borkowski, 1967, Loonstra 2001) For each letter, the participant is allowed one minute to generate the words. Performance is measured by the total number of correct words produced

summed across the three letters. Perseverations (i.e., repetitions of a correct word) and intrusions (i.e., words not beginning with the designated letter) are noted.

Although fluency tests are sensitive to language dysfunction and deterioration of semantic knowledge, they can also reflect an inability to initiate systematic retrieval of information in semantic storage. The COWAT will be administered at Baseline (Month 18 of TTP488-301), and at Months 6, 12, 18, and 24 or in the event of early termination.

Category fluency test (CFT): Study participants are given one minute to provide exemplars of the category ‘animals’. The CFT will be administered at Baseline (Month 18 of TTP488-301), and at Months 6, 12, 18, and 24 or in the event of early termination.

Trail Making Test, Parts A and B: (from the Halstead Reitan Neuropsychological Test Battery; Reitan, 1958). Part A consists of 25 circles numbered 1 through 25 semi-randomly distributed over a white sheet of 8 1/2" X 11" paper. The participant is instructed to connect the circles with a pencil line as quickly as possible in ascending numerical order. Part B also consists of 25 circles, but these circles are either numbered (1 through 13) or contain letters (A through L). Now the participant must connect the circles while alternating between numbers and letters in an ascending order (eg, A to 1; 1 to B; B to 2; 2 to C). Trails A and B are available in multiple forms of equal difficulty for purposes of repeated evaluations. The participant's performance can be judged in terms of the time (in seconds) required to complete each trail and by the number of errors of commission and omission. The time to complete Trails A (150 second maximum) and B (300 second maximum) will be the measures of interest. Whereas both Trails A and B depend on attention, visuomotor, and perceptual scanning skills, Trails B also requires considerable flexibility in shifting from number to letter sets under time pressure. Thus, participants who perseverate their current response set will encounter special difficulty with Trails B. The Trail Making Test (Parts A and B) will be administered at Baseline (Month 18 of TTP488-301), and at Months 6, 12, 18, and 24 or in the event of early termination.

7.2.2 Functional/Global Assessments

Alzheimer’s Disease Cooperative Study Activities of Daily Living Scale (ADCS-ADL): The ADCS-ADL is an activity of daily living inventory developed by the ADCS to assess functional performance in participants with AD (Galasko et al., 1997). Informants are queried via a structured interview format as to whether participants attempted each item in the inventory during the preceding 4 weeks, as well as their level of performance. The ADCS-ADL will be

administered at Baseline (Month 18 of TTP488-301), and at Months 6, 12, 18, and 24 or in the event of early termination. Scores range from 0-78 with lower scores indicating greater functional impairment.

Clinical Dementia Rating Scale (CDR): The CDR scale is used as a global measure of dementia and is completed by a clinician in the setting of detailed knowledge of the individual patient collected from interviews with the patient and caregiver (Berg, 1988). The CDR describes 5 degrees of impairment in performance on each of 6 categories including memory, orientation, judgment and problem solving, community affairs, home and hobbies, and personal care. Much of the information will therefore already have been gathered, either as part of normal clinical practice or as part of a research study. The interview takes approximately 40 minutes to administer.

CDR ratings are 0 for healthy individuals, 0.5 for questionable dementia and 1, 2 and 3 for mild, moderate and severe dementia as defined in the CDR scale. The scores for each category can also be summed and this is known as the sum of box score (CSR-SB). Sum of box scores range from 0 to 18 with higher scores indicating greater cognitive impairment.

The CDR will be conducted at Baseline (Month 18 of TTP488-301) and at Months 6, 12, 18, and 24 or in the event of early termination. CDR may be done on a separate proximal visit day to avoid patient fatigue.

